4.5 End of Study

Individual subject study completion is determined by completing the last visit in the Schedule of Activities (See Section 1.3). The study duration for each subject includes up to 21 days for screening, followed by a variable treatment **period**, and there is a SFU of **60 (+ 5)** days after the last tarlatamab dose, and a LTFU that spans up to 1 year after the last subject's last dose of tarlatamab or 5 years from first subject enrolled, whichever is first. **The study duration for subjects will be approximately up to 24 months, however, this duration will be extended as needed to ensure all subjects have the**

opportunity to be followed in LTFU for at least 1 year after the last subject's last dose of tarlatamab.

5. Study Population

Investigators will be expected to maintain a screening log to record details of all subjects screened that includes limited information about the screened subject (eg, date of screening). This log may be completed and updated via an Interactive Response Technology (IRT).

Eligibility criteria will be evaluated during screening.

Before any study-specific activities/procedures, the appropriate written informed consent must be obtained (see Section 11.3).

Prospective approval of protocol deviations to recruitment and enrollment criteria, also known as protocol waivers or exemptions, will not be provided.

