8.4.6.1.2 Serious Adverse Events

The investigator is responsible for ensuring that all serious adverse events observed by the investigator or reported by the subject that occur after signing of the informed consent through the SFU visit **or 60 days after the last dose of study treatment, whichever is later**, are recorded in the subject's medical record and are submitted to Amgen or its designee using the Events CRF.

Disease progression and death due to disease progression of SCLC are not considered serious adverse events and will not be reported as serious adverse event **unless there is evidence as suggesting a causal relationship between the investigational product(s) and/or noninvestigational product(s)/auxiliary medicinal product(s) and progression or symptom/sign of progression of the SCLC** as indicated in Section 11.4. Progression of the subject's underlying malignancy will be recorded in the Tumor Response CRF page as part of efficacy data collection and not on the Events CRF. Death due to disease progression is to be recorded in the End of Study CRF page and not on the Events CRF.

All serious adverse events will be collected, recorded, and reported to the sponsor or designee immediately and no later than 24 hours of the investigator's awareness of the event, as indicated in Section 11.4. The investigator will submit any updated serious adverse event data to the sponsor immediately and no later than 24 hours of it being available.

Since the criteria of the CTCAE grading scale differs from the regulatory criteria for serious adverse events, if adverse events correspond to grade 4 CTCAE toxicity grading scale criteria (eg, laboratory abnormality reported as grade 4 without manifestation of

life-threatening status), it will be left to the investigator's judgment to also report these abnormalities as serious adverse events. For any adverse event that applies to this situation, comprehensive documentation of the event's severity must be recorded in the subject medical records.

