3.1 Study Design

This is a phase 2a, multicenter, single arm, open-label study in Chinese subjects with advanced SCLC who have progressed on or recurred following 1 platinum-based regimen as 1L therapy (including a PD-1/PD-[L]1) and at least 1 other prior line of therapy (re-treatment with a platinum-based regimen is considered a second line of therapy). The study consists of a 21-day screening period, a treatment period, a safety follow-up (SFU) period, and a long-term follow-up (LTFU) period.

A SFU visit will occur 60 (+ 5) days after the last dose of tarlatamab regardless of initiation of subsequent anticancer therapy within that period. After the SFU visit,

subjects will be followed in LTFU for survival every 12 weeks (+/-14 days) for up to 1 year after the **last** subject's last dose of tarlatamab or 5 years from the first subject enrolled, whichever occurs first.

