- Date Collected on Reproductive Status and Pregnancy Test (Local Lab), Chemistry (Local Lab), Hematology (Local Lab), Coagulation (Local Lab) CRFs, Urinalysis (Local Lab) and in central lab data
- Start Date, Stop Date on Product Administration CRF
- Start Date, Stop Date on Other Protocol Required Therapy CRF
- Date Started and Date Ended on Events CRF for non-fatal events
- Tumor response and NYHA Classification date
- Target/non-target assessment date
- CRS Symptoms and ICANS date

- End of study, end of safety follow-up and end of administration date where end reason is not death or lost to follow-up
- Start date, Stop date on On-Study Radiotherapy, Anti-Cancer Therapies (Subsequent) CRF
- Subject Status Date if status is Alive on Survival Status CRF
- Assessment Date of CT or MRI
- Date of Liver biopsy
- Neurological Evaluation date
- Date of Clinical Outcome Assessments
- If death happened, then last known alive date is death date minus 1.
- Date of Anti-body sample
- Date of PK sample
- Date/Time of Tumor Measurement
- Date/Time of Tumor Identification
- Date/Time of Response Assessment

End of IP Administration

End of IP administration for each subject is defined as the date the decision was made to end IP as recorded on the End of Product Administration eCRF page.

End of Study Date (End of Trial)

The end of study date for the entire study is defined as the date when the last subject across all sites is assessed or receives an intervention for evaluation in the study (ie, last subject last visit) including any additional parts in the study (eg, LTFU, antibody testing), as applicable.

End of Study (Individual Subject)

End of study for each subject is defined as the date the subject last completed a protocol specified procedure. The date will be recorded on the End of Study eCRF page.

Safety Follow-up (SFU)

Upon permanent discontinuation from the study treatment for any reason, a safety follow up visit will be performed approximately 60 (+ 5) days after the end of the last dose of tarlatamab, regardless of initiation of subsequent anticancer therapy within that period.

Long Term Follow-up (LTFU)

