Following the SFU visit (60 [+ 5] days), subjects will enter the LTFU period for clinical evaluation of disease status and survival. Subjects will be followed via telephone, clinic visit, or chart review to assess for survival and/or the commencement of subsequent cancer therapy every 12 weeks (\pm 14 days) from the SFU visit or last imaging visit, whichever is later, for up to 1 year after the last subject's last dose of tarlatamab or 5 years from first subject enrolled, whichever occurs first.

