5.3 Safety Endpoint-related Definitions

Treatment-Emergent Adverse Event (TEAE)

TEAE is defined as adverse events starting on or after first dose of tarlatamab as determined by "Did event start before first dose of investigational product" equal to "No" or missing on the Events eCRF, and up to and including 65 days after the last dose of tarlatamab excluding the events reported after End of Study date. Events that are directly related to lung cancer or disease progression (including, but not limited to, preferred terms "Small cell lung cancer", "Disease progression" etc.) will be excluded from TEAE analysis.

Treatment-related Adverse Event (TRAE)

TRAE is defined as TEAE with the relationship flag on the Events eCRF indicating there is a reasonable possibility that the event may have been caused by tarlatamab. Event with missing relationship with tarlatamab is assumed to be treatment-related.

6. Analysis Sets

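### The TEAE definition excludes events reported after an End of Study date that it does not identify; on the subject-level reading this can drop serious or fatal events inside the 65-day window, on the trial-level reading almost nothing

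*SAP*

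**What the plan says.** SAP 5.3 opens the TEAE window at the first dose and runs it "up to and including 65 days after the last dose of tarlatamab excluding the events reported after End of Study date". A separate sentence in the same definition removes events directly related to lung cancer or its progression. TRAEs are defined as a subset of TEAEs.

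SAP 5.1 has two entries that could supply the date:

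- Trial level: "The end of study date for the entire study is defined as the date when the last subject across all sites is assessed"; a last intervention counts too, and long-term follow-up is included.
- Subject level: "End of study for each subject is defined as the date the subject last completed a protocol specified procedure", recorded on the End of Study eCRF page.

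SAP 5.3 points to neither. SAP 9.6.2 builds the serious, fatal, grade 3 or higher and events-of-interest summaries from treatment-emergent events only. On collection, Protocol 8.4.6.1.2 requires all serious adverse events "that occur after signing of the informed consent through the SFU visit", extended to day 60 from the last dose if that is later. Protocol 8.4.6.1.3 keeps related serious events reported after study end in the safety database.

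**The concern.** The 65-day limit already closes the window. A second stop can only take events away, and on the subject-level date it takes them from subjects whose participation ended early. Someone dosed at a visit who falls ill at home and dies before the next one has that dosing visit as the last completed procedure. Read literally, the event that ended participation is not treatment-emergent.

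The clause also turns on when an event is reported, not when it began. An event that started before the last procedure but reached the sponsor afterwards is exposed as well.

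TEAE incidence is the plan's safety and tolerability endpoint, so any loss would lower the serious, fatal, grade 3 or higher and related counts, and never raise them.

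**Working it through.** **Plan's own figure.** SAP 3.2 gives a 79% to 96% chance of seeing at least one adverse event in 30 subjects at true rates of 5% to 10%. The formula is 1 − (1 − p)^30:

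- p = 0.05: 1 − 0.95^30 = 78.5%
- p = 0.10: 1 − 0.90^30 = 95.8%

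Both reproduce. The calculation assumes that every event that occurs is counted.

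**Test case (hypothetical).** The subject is dosed and examined on day 0 and completes no later procedure. A non-progression event begins on day 10 and the subject dies on day 14. The site learns of it and reports on day 15. Day 10 is inside the 65-day TEAE window and inside the protocol's collection period.

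| End of Study date applied | Judged by report date (day 15) | Judged by onset date (day 10) |
|---|---|---|
| Subject level as defined: last procedure, day 0 | dropped | dropped |
| Subject level, recorded as death date, day 14 | dropped | kept |
| Trial level: last subject, last visit | kept | kept |

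Three of the six readings drop the event. The literal subject-level definition drops it on either basis.

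**Who is exposed.** Safety follow-up is set so that "A SFU visit will occur 60 (+ 5) days after the last dose of tarlatamab". Long-term contacts then "assess for survival and/or the commencement of subsequent cancer therapy every 12 weeks". A subject with any contact after day 65 has a last procedure beyond the window and is generally unaffected. That leaves subjects who die, withdraw or are lost before such a contact, including the gap between a day-60 visit and day 65 when nothing follows.

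**When each date exists.** SAP 7.2 places the primary analysis once all subjects have had the opportunity to confirm a response, or at up to 13 weeks of follow-up. Long-term follow-up can run to 1 year after the last subject's last dose (SAP 3.1). The trial-level date will therefore normally not exist at the primary analysis, whereas the subject-level date is on the eCRF for anyone who has left.

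**Size of one lost event (illustration).** With n = 30, one subject is 1/30 = 3.3 percentage points. Clopper-Pearson 95% upper limits:

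- 0/30: 1 − 0.025^(1/30) = 11.6%
- 1/30: 97.5th percentile of Beta(2, 29) = 17.2%

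**Effect on detection (assumed loss; the documents give no rate).** If a fraction f of affected subjects went uncounted, the probability becomes 1 − (1 − p(1 − f))^30:

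| f | p = 5% | p = 10% |
|---|---|---|
| 0 | 78.5% | 95.8% |
| 10% | 74.9% | 94.1% |
| 25% | 68.2% | 90.4% |
| 50% | 53.2% | 78.5% |

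SAP 9.6.2 also drops a summary when two or fewer subjects have the event, so losing one subject of three can remove a table.

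**The case against.** The other side has four good points.

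- The wording in SAP 5.3 sits closer to the trial-level entry, the only one of the two with the word date in its heading. A trial-level cut has a plausible purpose as a data-closure rule, because Protocol 8.4.6.1.3 sends later reports to the safety database.
- For a death, the recorded subject-level date may be the date of death. The last-known-alive list in SAP 5.1 accepts "End of study, end of safety follow-up and end of administration date where end reason is not death or lost to follow-up", which suggests that end dates for deaths are not dates on which the subject was known to be alive. The protocol's own rule, "Individual subject study completion is determined by completing the last visit in the Schedule of Activities", does not settle the matter for someone who dies between visits.
- The event attributes in Protocol 11.4 include onset and resolution dates but no report date, so a programmer might well use onset.
- Protocol 11.4 leaves the TEAE definition to the SAP, so the clause does not contradict the protocol.

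All four stand, and they rule out a stronger reading: a reader might infer that the plan definitely removes fatal events from the safety tables. The documents do not show that, because the date is not identified. Nor can the loss be sized from the 68% nine-month survival in Protocol 2.3. That figure gives 30 × (1 − 0.68) = 9.6 deaths, but it is all-cause survival from another study, and it includes progression deaths and deaths more than 65 days after the last dose.

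What these points do not do is defend the clause. Each relies on the programmer choosing the harmless interpretation, and the death-date reading departs from the literal definition in SAP 5.1.

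**Conclusion.** The point holds as an unresolved definition with a one-directional consequence. On the trial-level date the clause is nearly void. On the subject-level date as written, it removes non-progression events, including serious and fatal ones, first reported after the last visit although they began within 65 days of the last dose. Neither outcome is a reason to keep it.

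The number of events at risk is unknown. What would be lost is their place in the TEAE, TRAE and events-of-interest tables: serious events remain in the safety database and deaths still count in overall survival. The change from 1/30 to 0/30 shows only what a single loss would do at this sample size; it does not estimate the expected loss.

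**What to change.** In SAP 5.3, delete the exclusion tied to End of Study. Define a TEAE by onset, from first dose through 65 days after the last dose, and keep the existing exclusion of progression events. Onset date is already a mandatory event attribute (Protocol 11.4), and SAP Appendix A already covers partial or missing start dates, so no new data are needed.

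If the sponsor wants a further stop, name the trial-level date or withdrawal of consent to data collection, and apply it to onset rather than report date. Do not replace the clause with a blanket rule that keeps every event up to death: that would admit pre-dose events, progression events and events after day 65.

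The cost is one sentence of SAP text and one line of derivation code, best settled before the primary-analysis lock. The downside is that fatal and serious TEAE counts may be slightly less favourable.

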
 Any abnormal laboratory test results (hematology, clinical chemistry, or urinalysis) or other safety assessments (eg, electrocardiogram [ECG], radiological scans, vital signs measurements), including those that worsen from baseline, that are considered clinically significant in the medical and scientific judgment of the investigator (ie, not related to progression of underlying disease). Exacerbation of a chronic or intermittent preexisting condition including either an increase in frequency and/or intensity of the condition. New conditions detected or diagnosed after study treatment administration even though it may have been present before the start of the study. Signs, symptoms, or the clinical sequelae of a suspected drug-drug interaction. Signs, symptoms, or the clinical sequelae of a suspected intentional overdose of either study treatment or a concomitant medication. Intentional overdose will be reported as an adverse event/serious adverse event when it is taken with possible suicidal/self-harming intent. Such intentional overdoses are to be reported regardless of sequelae on the Events CRF. Accidental/unintentional overdose will be captured as a medication error. Disease progression is an efficacy endpoint. Progression or symptom/sign of the small cell lung cancer (SCLC) should ONLY be reported as an adverse event or serious adverse event if there is evidence suggesting a causal relationship between the investigational product(s) and/or noninvestigational product(s)/auxiliary medicinal product(s) and progression or symptom/sign of progression of the SCLC. The event should be recorded on the Events CRF. “Lack of efficacy” or “failure of expected pharmacological action” per se will not be reported as an adverse event or serious adverse event. Such instances will be captured in the efficacy assessments.
Events NOT Meeting the Adverse Event Definition

 Medical or surgical procedure (eg, endoscopy, appendectomy): the condition that leads to the procedure is the adverse event.

- Situations in which an untoward medical occurrence did not occur (social and/or convenience admission to a hospital).
- Anticipated day-to-day fluctuations of preexisting disease(s) or condition(s) present or detected at the start of the study that do not worsen.

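### The TEAE definition removes progression and lung-cancer events whatever their relationship flag, although the protocol admits such events as adverse events only when study product is a suspected cause

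*SAP*

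**What the plan says.** **Protocol, what enters the data.** Section 11.4 (Appendix 4), in the list of events that meet the adverse event definition, says that progression of SCLC, or a symptom or sign of it, "should ONLY be reported as an adverse event or serious adverse event if there is evidence suggesting a causal relationship" with investigational or non-investigational product. It then adds: "The event should be recorded on the Events CRF". Section 8.4.6.1.2 applies the same rule to serious and fatal events: "Disease progression and death due to disease progression of SCLC are not considered serious adverse events and will not be reported as serious adverse event", followed by the same causality exception. Sections 8.4.6.1.1 and 8.4.6.1.3 repeat the exception for adverse events and for serious events found after the reporting period.

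**SAP, what is analysed.** Section 5.3 takes a class of events, "Events that are directly related to lung cancer or disease progression (including, but not limited to, preferred terms" (small cell lung cancer and disease progression are the two examples given), and states that they "will be excluded from TEAE analysis". It gives no exception for events flagged as related. In the same section, "TRAE is defined as TEAE with the relationship flag on the Events eCRF" pointing to tarlatamab, and a missing relationship counts as related.

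**What the tables are built on.** The adverse event summaries in SAP Section 9.6.2 (all, related, serious, grade 3 or higher, fatal, leading to withdrawal, leading to interruption or reduction) are summaries of TEAEs or TRAEs. The events of interest are treatment-emergent as well. No listing of the excluded events is planned.

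**The concern.** Many oncology plans keep disease progression out of the adverse event tables so that the disease is not counted as toxicity. This protocol already does that at the point of reporting: ordinary progression is not to be reported as an adverse event. What its rule leaves for the adverse event data is progression that someone had reason to link to study product. A second, unconditional filter in the SAP then acts on that remainder.

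Safety and tolerability are a secondary objective, measured by TEAE incidence. The protocol leaves the TEAE definition to the SAP, and its Section 9.4.2.3.1 calls for tables of all TEAEs with separate serious, fatal and treatment-related tables. A suspected drug-related progression event, possibly a fatal one, that was reported exactly as instructed would appear in none of them.

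**Working it through.** **1. The plan's own safety figure.** Protocol Section 9.2 and SAP Section 3.2 give a 79% to 96% chance of at least one adverse event among 30 subjects at a true rate of 5% to 10%. With P(X ≥ 1) = 1 − (1 − p)^30:
- p = 0.05: 1 − 0.95^30 = 78.5%
- p = 0.10: 1 − 0.90^30 = 95.8%

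The figure reproduces and is not in dispute. It presumes that an event, once it occurs, can appear in a table.

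**2. One event followed through the rules.** Take a progression event that the investigator suspects was caused by tarlatamab, coded to one of the two terms named in the SAP.
- Protocol 11.4: the causality condition is met, so it goes on the Events CRF with a relationship assessment, which is a mandatory attribute.
- SAP 5.3, TEAE: the event is of the excluded class. The relationship flag is not consulted, so it is not a TEAE.
- SAP 5.3, TRAE: a TRAE must first be a TEAE, so it is not a TRAE, although the flag says related.
- SAP 9.6.2: the serious, grade 3 or higher, fatal and withdrawal summaries count TEAEs, so it is absent from each.
- SAP 9.6.2 fallback: when two or fewer subjects have an event, subject-level data may replace the summary. That replaces the same TEAE and TRAE summaries, so it does not bring the event back.

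**3. Size.** The documents give no expected count, so the number of affected subjects, x, is assumed here to run from 0 to 3 of 30. The exact 95% limits are Clopper-Pearson: the lower limit is the 0.025 quantile of Beta(x, 31 − x) and the upper limit the 0.975 quantile of Beta(x + 1, 30 − x).

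| Affected subjects | Shown under SAP 5.3 | Shown if kept (exact 95% CI) |
|---|---|---|
| 0 | 0/30 | 0/30 = 0% (0% to 11.6%) |
| 1 | 0/30 | 1/30 = 3.3% (0.1% to 17.2%) |
| 2 | 0/30 | 2/30 = 6.7% (0.8% to 22.1%) |
| 3 | 0/30 | 3/30 = 10.0% (2.1% to 26.5%) |

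The middle column is the count of these events. It is zero whatever the true number.

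**The case against.** **The filter may be meant as data cleaning.** The list in Protocol 11.4 of events that do not meet the adverse event definition says, without any exception, that RECIST progression, its expected symptoms and deaths attributed to it are not adverse events. The sections under 8.4.6.1 also follow their exception with a sentence that sends progression to the tumor response form and not the Events CRF. Appendix 8 lists small cell lung cancer and metastasis among serious events anticipated regardless of exposure. Non-causal entries may therefore reach the data, and removing them is reasonable. This stands as a limit: that only drug-suspected progression events are recorded is the reporting rule, not a known fact about the data. It does not rescue the filter, which also removes the properly reported causal events.

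**The wording leaves room.** A suspected drug-related symptom coded to its own preferred term is not clearly excluded, and one could argue that an event judged to be caused by tarlatamab is not directly related to lung cancer. That is fair. The gap is plainest for the two named terms. The list of terms is also open-ended, but nothing in the documents shows that it would be used to remove terms after the data are seen; that is a secondary missing detail.

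**Reach.** A reader might infer that these events vanish from all safety output. The documents do not support that. Laboratory, vital-sign, exposure and antibody outputs do not depend on TEAEs. Deaths still count in OS, progression and death still count in PFS subject to its censoring rules, and expedited SAE reporting is unchanged.

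**End of Study clause.** A reader might also infer that fatal events are lost because the TEAE definition drops events reported after the End of Study date, and SAP 5.1 has a subject-level definition: "End of study for each subject is defined as the date the subject last completed a protocol specified procedure". But the TEAE wording matches the other heading in SAP 5.1, the trial-level End of Study Date, which includes long-term follow-up. On that reading the 65-day window is rarely if ever cut. Loss through this clause is not established.

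**Conclusion.** The concern holds for the adverse event incidence tables. If the SAP is followed as written, a progression or SCLC event reported because of suspected causality is missing from the TEAE, TRAE, serious, grade 3 or higher and fatal summaries. Each such subject is 3.3 percentage points with 30 subjects. The number affected is unknown and may be zero.

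The conclusion rests on two assumptions: that sites apply the causality exception in Protocol 8.4.6.1 and 11.4, and that the event is coded to a term the SAP treats as lung cancer or progression. Because the exception also covers non-investigational products, not every lost event would have been a tarlatamab TRAE. The study is single-arm and descriptive, and the primary ORR analysis is untouched. The case for correction is that the tables cannot show the progression events the protocol asks to have reported.

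**What to change.** In SAP Section 5.3:
- Exclude progression and SCLC preferred terms from TEAE only when relationship to tarlatamab and to the other study products is recorded as No.
- Keep events flagged related, or with relationship missing, in the TEAE, serious and fatal tables. Count them as TRAE when the tarlatamab flag is yes or missing, in line with the SAP's existing rule for missing relationship.
- Add a listing of all excluded events, so that the effect of the open-ended term list can be seen.

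In the protocol, reconcile the unconditional list of non-adverse events in Section 11.4 with the causality exception in Sections 8.4.6.1.1 to 8.4.6.1.3 and in the preceding list of 11.4, including which form the event goes on. No change to the End of Study clause is proposed.

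The relationship assessments are already mandatory on the Events CRF, so the SAP change needs no new data. The cost is SAP wording, one listing and a protocol clarification. The downside is that reported adverse event rates may be slightly higher.
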